4.2. Scientific rationale for study design

This Phase 2a study of VH3739937 will be conducted in HIV-1 infected, TN participants to decrease the possibility of participants experiencing viral resistance to VH3739937. Dosing with VH3739937 will be limited to 7 days of monotherapy as an additional measure to decrease the probability of development of resistance to VH3739937.

CCI

CCI

[REDACTED] On Day 8, all participants will switch to combination antiretroviral therapy selected by the investigator and remain on study for evaluation based on the elimination of the majority of VH3739937 which is anticipated to be achieved approximately 18 days after the last dose of VH3739937.

There are no commercially available/approved MIs nor is there evidence of cross-class resistance (e.g. as occurs for protease inhibitors) therefore dosing with VH3739937 will not interfere with selection of the cART regimen selected by the investigator on Day 8 and any subsequent regimen following completion of the study.

The justification for the use of a placebo control allows for blinded assessment of relationship to a treatment emergent adverse event. One placebo cohort of 2 participants will facilitate blinded assessment of safety and tolerability. Since Investigators and participants will be blinded, any safety event (AE, lab abnormality, ECG abnormality, etc) will be evaluated and managed in the same fashion. Further, there is no evidence that delaying initiation of cART by 7 days in a TN study participant will adversely impact the short and long term clinical outcomes following the initiation of cART [Egger, 2002].

4.2.1. Participant input into design

This is the first study of VH3739937 in people living with HIV-1. Participants were not engaged in development of the study design which is consistent with other Proof of Concept Phase 2a studies of antiretroviral therapies.

[figure not shown]
4.3. Justification for dose

CCI

CONFIDENTIAL

212580
Protocol Amendment 1 Final

CCI

CCI

4.4. End-of-study definition

A participant is considered to have completed the study if the participant has completed all periods of the study including the last scheduled procedure shown in the SoA.

The end of the study is defined as the date of the last visit of the last participant in the study.

Part 2 of the study is optional. Completion of the study at the end of Part 1 will not be considered an early termination.

5. STUDY POPULATION

Prospective approval of protocol deviations to recruitment and enrollment criteria, also known as protocol waivers or exemptions, is not permitted.

5.1. Inclusion criteria

Participants are eligible to be included in the study only if all of the following criteria apply:

Age

1. Participant must be 18 to 65 years of age inclusive at the time of signing the informed consent.

Type of Participant and Disease Characteristics

2. Participants who are overtly healthy (other than HIV infection) as determined by the Investigator or medically qualified designee based on a medical evaluation including medical history, physical examination, laboratory tests, and cardiac monitoring.
3. Screening CD4+ T-cell count ≥ 200 cells/mm³
4. Documented HIV infection and Screening plasma HIV-1 RNA ≥ 3000 ($\geq 3.48 \log_{10}$) and $< 1,000,000$ ($< 6.0 \log_{10}$) copies/mL. A single repeat of this test is allowed within a single Screening period to determine eligibility.
5. Positive HIV antibody test
6. Treatment-naïve: No ARVs (in combination or monotherapy) received after the diagnosis of HIV-1 infection.

Weight

7. Body weight ≥ 50.0 kg (110 lbs.) for men and ≥ 45.0 kg (99 lbs) for women and BMI for all participants within the range 18.5-35.0 kg/m².

Sex and Contraceptive/Barrier Requirements

8. All participants in the study should be counseled on safer sexual practices including the use and benefit/risk of effective barrier methods (e.g., male condom) and on the risk of HIV transmission to an uninfected partner.

*NOTE: There are no contraceptive requirements for participants who were male at birth.

Participants Female at birth:

A participant who was female at birth is eligible to participate if they are a PONCBP (see [Appendix 4](#)).

Note: The investigator is responsible for review of medical history, menstrual history, and recent sexual activity to decrease the risk for inclusion of a woman with an early undetected pregnancy.

Informed Consent

9. Capable of giving signed informed consent as described in Section [10.1](#), which includes compliance with the requirements and restrictions listed in the informed consent form and stated in this protocol.

Other Inclusions

10. Participant must be willing and able to start cART as selected with the Investigator on Study Day 8 (except in the case of early termination, clinically relevant AE/SAE, lab abnormality, the withdrawal of consent, lost to follow-up, etc., where circumstances could dictate otherwise).

5.2. Exclusion criteria

Participants are excluded from the study if any of the following criteria apply:

Medical Conditions

1. Any evidence of an active Centers for Disease Control and Prevention (CDC) Stage 3 disease [[CDC](#), 2014], except cutaneous Kaposi's sarcoma not requiring systemic therapy during the study;
2. Ongoing malignancy other than cutaneous Kaposi's sarcoma, basal cell carcinoma, or resected, non-invasive cutaneous squamous cell carcinoma, or cervical, anal or penile intraepithelial neoplasia; or other localized malignancies require agreement between the investigator and the study medical monitor for inclusion of the participant prior to randomization. Treatment with radiation therapy or cytotoxic chemotherapeutic agents within 30 days of study drug administration or anticipated need for such treatment within the study;
3. Any history of significant underlying psychiatric disorder, in the opinion of the Investigator or Medical Monitor, including but not limited to schizophrenia, bipolar disorder with or without psychotic symptoms, other psychotic disorders, or schizotypal (personality) disorder; or a clinical assessment of suicidality based on the responses on the C-SSRS. Participants' history of suicidal behaviour and/or suicidal ideation should be considered when evaluating for suicide risk;
4. Any history of major depressive disorder with or without suicidal features, or anxiety disorders, that required medical intervention (pharmacologic or not) such as hospitalization or other inpatient treatment and/or chronic (>6 months) outpatient treatment;

Note: Participants with other conditions such as adjustment disorder or dysthymia that have required shorter term medical therapy (<6 months) without inpatient treatment and are currently well-controlled clinically or resolved may be considered for entry after discussion and agreement with the Medical Monitor.

5. Any pre-existing physical or other psychiatric condition (including alcohol or drug abuse) which, in the opinion of the Investigator or Medical Monitor (with or without psychiatric evaluation), may interfere with the participant's ability to comply with the dosing schedule and/or protocol evaluations or which may compromise the safety of the participant;
6. Current or chronic history of liver disease or known hepatic or biliary abnormalities (with the exception of Gilbert's syndrome or asymptomatic gallstones);
7. Participants with primary HIV infection, evidenced by acute retroviral syndrome (e.g., fever, malaise, fatigue, etc) and/or evidence of recent (within 3 months)

documented viremia without antibody production and/or evidence of recent (within 3 months) documented seroconversion;

8. A pre-existing condition, in the opinion of the Investigator or Medical Monitor, that could interfere with normal gastrointestinal anatomy or motility (e.g., GERD, gastric ulcers, gastritis, inflammatory bowel disease), hepatic and/or renal function, that could interfere with the absorption, metabolism, and/or excretion of the study interventions or render the participant unable to take oral study treatment;
9. Myocardial infarction, acute coronary syndrome, unstable angina, stroke, transient ischemic attack, or intermittent claudication in the past 3 months;
10. Medical history of cardiac arrhythmias or cardiac disease or a family or personal history of long QT syndrome or sudden cardiac death. Any significant arrhythmia or ECG finding which, in the opinion of the Investigator or Medical Monitor, will interfere with the safety for the individual participant;
 - Examples of ECG findings include symptomatic bradycardia, non-sustained or sustained atrial arrhythmias, non-sustained VT or sustained VT, AVB Mobitz Type II, or third degree AVB.

Prior/Concomitant Therapy

11. Prior exposure to a MI
12. Treatment with immunomodulating agents (such as systemic corticosteroids, interleukins, interferons) or any agent with known anti-HIV activity (such as hydroxyurea or foscarnet) within 30 days of study drug administration. If patients received ARV(s) for PrEP inadvertently after their diagnosis of HIV-1, they cannot screen for this trial until 5 half-lives have elapsed.
13. Past or intended use of over-the-counter or prescription medication including herbal medications within 7 days (or 14 days if the drug is a potential enzyme inducer) or 5 half-lives (whichever is longer) prior to dosing. Specific medications listed in Section 6.8 may be allowed;
14. History of sensitivity to any of the study medications, or their components or drugs of their class, or a history of drug or other allergy that, in the opinion of the investigator or Medical Monitor, contraindicates their participation. Participants who require concomitant medications known to be associated with a prolonged QTc;
15. Treatment with any of the following agents within 28 days of Screening: radiation therapy, cytotoxic chemotherapeutic agents, any systemic immune suppressant;
16. Participants receiving any protocol-prohibited medication and who are unwilling or unable to switch to an alternate medication;

Prior/Concurrent Clinical Study Experience

17. The participant has received an investigational HIV vaccine (immunotherapeutic or immunomodulatory);

18. Exposure to an experimental drug or experimental vaccine within either 28 days, 5 half-lives of the test agent, or twice the duration of the biological effect of the test agent, whichever is longer, prior to the first dose of study intervention;

Diagnostic Assessments

19. Untreated syphilis infection [positive RPR at screening] without documentation of treatment. Participants who have successfully completed treatment at least 7 days previously are eligible if recruitment is open;

20. QTc >450 msec or QTc > 480 msec in participants with bundle branch block

21. Exclusion criteria for screening ECG (a single repeat is allowed in some instances for eligibility determination):

Heart Rate <50 or >100 bpm, or QTcF >450 msec;

Notes:

- A heart rate <50 or >110 bpm is exclusionary and cannot be rechecked to determine eligibility.
- A heart rate from 101-110 bpm can be checked by a single repeat ECG or by vital signs within 30 minutes to verify eligibility.
- The QTc is the QT interval corrected for heart rate according to Fridericia's formula (QTcF). It is either machine-read or manually over-read by the Investigator. QTcF is used to determine eligibility and discontinuation for an individual participant in this study. The Investigator's or Medical Monitor's over-read can supercede that of the machine at any time.

22. Presence of HBsAg or HBcAb at screening

Note: Evidence of HBV infection based on the results of testing at Screening for HBsAg:

- Patients who are negative for HBsAg should also be tested for anti-HBc, anti-HBs and HBV DNA and excluded according to the following algorithm:
 - Participants negative for anti-HBs but positive for anti-HBc (negative HBsAg status) and positive for HBV DNA are excluded
 - Participants positive for anti-HBc (negative HBsAg status) and positive for anti-HBs (past and/or current evidence) are immune to HBV and are not excluded.

Note: HBV DNA testing will only be performed during screening and prior to randomisation for participants with positive anti-HBc and both negative HBsAg and anti-HBs (past and/or current evidence).

23. Positive Hepatitis C antibody test result at screening AND positive on reflex to Hepatitis C RNA

Note: Participants with positive Hepatitis C antibody due to prior resolved disease can be enrolled only if a confirmatory negative Hepatitis C RNA test is obtained (central lab will automatically reflex to HCV RNA on positive HCVAb)

24. Any Grade 2-4 laboratory abnormality at Screening, with the exception of CPK and lipid abnormalities (e.g., total cholesterol, triglycerides, etc), ALT (described below) and eGFR, will exclude a participant from the study unless the investigator can provide a compelling explanation for the laboratory result(s) and has the assent of the sponsor. A single repeat of any lab abnormality is allowed within a single Screening period to determine eligibility;
25. ALT $\geq 1.5 \times$ ULN or total bilirubin $\geq 1.5 \times$ ULN. A single repeat of ALT and / or bilirubin is allowed within a single Screening period to determine eligibility;
26. Any acute laboratory abnormality at screen which, in the opinion of the investigator, should preclude participation in the study of an investigational compound;
27. eGFR of $< 50 \text{ mL/min/1.73 m}^2$ via CKD-EPI 2021 method;
28. Any positive result for illicit drug use (e.g., cocaine, heroin) at Screening. A positive screen for marijuana / THC is not exclusionary, see Section [5.3.2](#) for guidance to be given to the participant.

Other Exclusion Criteria

29. Regular use of drugs of abuse
30. Sensitivity to heparin or heparin-induced thrombocytopenia

5.3. Lifestyle considerations

5.3.1. Meals and dietary restrictions

Participants will be required to fast for at least 8 h [overnight] prior to the morning check-in at clinic visits on Days 1-8 and Day 25 in Part 1A (and optional Part 2A) and Days 1, 8 and 25 in Part 1B (and optional Part 2B). Procedures will be performed in the following order: C-SSRS, ECG, Vital Signs and Blood Draws in a fasted state. On days when participants take the study intervention, each dose will be taken with approximately 240 mL (8 ounce) water following ingestion of a moderate calorie and fat meal, to be completed within approximately 25 minutes just prior to dosing, with dose administration to occur within 5 minutes of completion of meal consumption. This includes the virtual visits where participants must have completed their meal within approximately 25 minutes of their scheduled call with site staff, with dose administration to occur within 5 minutes of completion of meal consumption.

Refrain from consumption of red wine, Seville oranges, grapefruit, or grapefruit juice, pomelos, exotic citrus fruits, grapefruit hybrids, or fruit juices from 3 days before the start of study intervention until Day 8.

5.3.2. Caffeine, alcohol, and tobacco

During the study alcohol consumption will be limited to the following: An average weekly intake of <14 drinks for participants assigned as male at birth or <7 drinks for participants assigned as female at birth. One drink is equivalent to 12 g of alcohol: 12 ounces (360 mL) of beer, 5 ounces (150 mL) of wine or 1.5 ounces (45 mL) of 80 proof distilled spirits.

No alcohol will be consumed on the in-clinic serial PK days (Day 1 and, if applicable, Day 7) until after the final assessment of the day and release from the clinic.

Only clinically minor to moderate use (as determined by the Investigator) of tobacco products will be allowed during study participation, with extremely limited use on the in-clinic serial PK days (Day 1 and, if applicable, Day 7).

Participants should refrain from the use of marijuana during the treatment period.

5.3.3. Activity

Participants will abstain from strenuous exercise during Days 1 to 8.

5.4. Screen failures

A screen failure occurs when a participant who has consented to participate in the clinical study is not subsequently randomized to study intervention. A minimal set of screen failure information is required to ensure transparent reporting of screen failure participants to meet the CONSORT publishing requirements and to respond to queries from regulatory authorities. Minimal information includes demography, screen failure details, eligibility criteria, information from any previous trials with the same IP, and any SAE.

Individuals who do not meet the criteria for participation in this study (screen failure) may be rescreened once if, in the opinion of the Investigator, the current clinical outlook of the participant is favorable for study inclusion.

Rescreened participants should be assigned a new participant number for every screening/rescreening event. Previously assigned participant numbers are to be record in the participants' CRF/eCRF. All screening procedures should be repeated at the rescreening visit.

5.5. Criteria for temporarily delaying enrollment/randomization/administration of study intervention

Not applicable

6. STUDY INTERVENTION(S) AND CONCOMITANT THERAPY

The definition of study intervention is provided in the table of definitions.

6.1. Study intervention(s) administered

Table 4 Study Intervention(s) Administered

| Intervention Label | | |
|--------------------------|--|---|
| Intervention on Label: | VH3739937 CCI [REDACTED] | Placebo to match VH3739937 CCI [REDACTED] |
| Intervention Description | CCI [REDACTED] | CCI [REDACTED] |
| Type | Drug | Drug |
| Dose Formulation: | CCI [REDACTED] | CCI [REDACTED] |
| Unit Dose Strength(s) | CCI [REDACTED] | N/A |
| Dosage Level(s): | Variable depending on dose | Variable depending on dose |
| Route of Administration | Oral | Oral |
| Dosing instructions: | CCI [REDACTED] | |
| Use | Experimental | Placebo |
| IMP and NIMP | IMP | IMP |
| Packaging and Labeling | Blinded Study Intervention will be provided in high-density polyethylene (HDPE) bottles which contain a desiccant. Each bottle will be labelled as required per country requirement. | Blinded Study Intervention will be provided in high-density polyethylene (HDPE) bottles which contain a desiccant. Each container will be labelled as required per country requirement. |
| Sourcing / Manufacturer | Provided centrally by the Sponsor | Provided centrally by the Sponsor |

| | | |
|---|------------|----------------|
| Current/Former Name(s) or Alias(es) | GSK3739937 | Not Applicable |
|---|------------|----------------|

6.2. Preparation, handling, storage, and accountability

The investigator or designee must confirm appropriate conditions (e.g., temperature) have been maintained during transit for all study intervention received, and any discrepancies are reported and resolved before use of the study intervention.

Only participants enrolled in the study may receive study intervention, and only authorized site staff may supply, prepare, or administer study intervention.

All study intervention must be stored in a secure, environmentally controlled, and monitored (manual or automated) area in accordance with the labeled storage conditions with access limited to the investigator and authorized site staff.

The investigator, institution, the head of the medical institution (where applicable), or authorized site staff is responsible for study intervention accountability, reconciliation, and record maintenance (i.e., receipt, reconciliation, and final disposition records).

Further guidance and information for the final disposition of unused study interventions are provided in the pharmacy manual.

Under normal conditions of handling and administration, study intervention is not expected to pose significant safety risks to site staff.

A MSDS/equivalent document describing occupational hazards and recommended handling precautions either will be provided to the investigator, where this is required by local laws, or is available upon request from ViiV Healthcare/GSK.

6.3. Assignment to study intervention

All participants will be centrally assigned to randomized study intervention according to a computer-generated randomization schedule provided by the Sponsor, using RAMOS NG. Before the study is initiated, the telephone number and call-in directions for RAMOS NG and/or the log-in information and directions for RAMOS NG will be provided to each site.

Participants will ideally be randomized within 14 days of the start of Screening; up to 28 days maximum may be allowed. In Part 1, 3 cohorts of approximately 6 participants will receive active doses of VH3739937 and 1 cohort of approximately 2 participants will receive placebo. As noted earlier, the dose(s)/frequency and exact arms/sample size for Part 2 are to be determined based upon a planned interim analysis of available preliminary unvalidated clinical data.

Study intervention will be dispensed at the study visits as summarized in the SoA.

Returned study intervention should not be re-dispensed to the participants.

6.4. Blinding

| | |
|-------------------------------|---|
| Emergency unblinding RAMOS NG | 
This is a double-blind study in which participants/care providers/investigators/outcomes assessors, etc. are blinded to study intervention. RAMOS NG will be programmed with blind-breaking instructions. In case of an emergency, the investigator has the sole responsibility for determining if unblinding of a participants' intervention assignment is warranted. Participant safety must always be the first consideration in making such a determination. If the investigator decides that unblinding is warranted, the investigator may, at the investigator's discretion, contact ViiV Healthcare/GSK to discuss the situation prior to unblinding a participant's intervention assignment unless this could delay emergency treatment for the participant. If a participant's intervention assignment is unblinded, ViiV Healthcare/GSK must be notified within 24 h of this occurrence. The date and reason for the unblinding must be recorded.
 
If the investigator is unable to access RAMOS NG, they can contact the GSK helpdesk based on the information provided in the pharmacy manual.
 
A physician other than the investigator (e.g., an emergency room physician) or participant/participant's caregiver or family member may also request emergency access to the participant's study intervention information as per participant card.
 |
|-------------------------------|---|

This early phase study of relatively small size will not use an external DMC. The ongoing monitoring of blinded study data including clinical safety, efficacy and PK data will be overseen by an experienced central ViiV Healthcare/GSK study team. This central study team will have access to unblinded data if indicated and, if appropriate, will discuss data in a blinded fashion when interacting with site staff. As a general principle during study

conduct, members of the ViiV Healthcare/GSK study team and other ViiV Healthcare/GSK staff will remain blinded unless unblinding becomes necessary.

A participant will be withdrawn if the participant's intervention code is unblinded by the investigator or treating physician. The primary reason for discontinuation (the event or condition which led to the unblinding) will be recorded in the eCRF.

ViiV Healthcare/GSK's Global Safety staff may unblind the intervention assignment for any participant with an SAE. If the SAE requires that an expedited regulatory report be sent to one or more regulatory agencies, a copy of the report, identifying the participant's intervention assignment, may be sent to investigators in accordance with local regulations and/or ViiV Healthcare/GSK policy.

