3. OBJECTIVES, ENDPOINTS AND ESTIMANDS

3.1. Objectives and Endpoints

Table 2 Objectives and Endpoints

[figure not shown]
| Objectives | Endpoints |
|---|--|
| Primary | |
| 
 To evaluate the antiviral activity of VH3739937 in HIV-1 infected TN participants during 7 days of monotherapy | 
 Maximum change from baseline (Day 1) in plasma HIV-1 RNA through Day 8 |
| Secondary | |
| 
 To assess the safety and tolerability of VH3739937 when administered as monotherapy over 7 days in HIV-1 infected TN participants | 
 Incidence of SAEs, Deaths and AEs leading to Discontinuation through Day 8 |
| 
 To characterize the pharmacokinetics of VH3739937 in HIV-1 infected TN participants | 
VH3739937 PK parameters :
 
Following QD dosing:
 
 Day 1: Cmax, tmax, C24 and AUC(0-24) Day 7: Cmax,ss, tmax, C24,ss and AUC(0-24),ss 
Following single dose: Cmax, tmax, AUC(0-168) and C168
 |
| Exploratory | |
| 
 To assess the safety and tolerability of VH3739937 when administered as monotherapy over time in HIV-1 infected TN participants | 
 Incidence of AEs and severity of AEs through Day 25 Change from baseline and maximum toxicity grade increase from baseline for liver panel laboratory parameters (consisting of total and direct bilirubin, ALT, ALP and AST) |
| 
 To assess the occurrence of Gag treatment emergent mutations or substitutions after 7 days of monotherapy with VH3739937 | 
 Genotypic assessment to detect any change in the Gag gene sequence from Day 1 to Day 8 |
| 
 To assess the immunologic effects of VH3739937 when administered over 7 days in HIV-1 infected adults | 
 Change from baseline in CD4+ T-cell count through Day 8 |

| | |
|--|---|
| 
• To characterize the pharmacokinetics of VH3739937 in HIV-1 infected TN participants | 
Additional VH3739937 PK parameters:
 
• Following QD dosing (Day 7 only): CL/F, V/F and t_{1/2} will be determined if possible• Following single dose: AUC(0-24) and C₂₄, In addition, AUC_{infinity}, CL/F, V/F and t_{1/2} will be determined where possible |

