7.2. Participant discontinuation/withdrawal from the study

A participant may withdraw from the study at any time at the participant's own request for any reason (or without providing any reason).

A participant may be withdrawn at any time at the discretion of the investigator for safety, behavioral, or compliance reasons.

Investigators will attempt to contact participants who do not return for scheduled visits or follow-up.

At the time of discontinuing from the study, if possible, an ED visit should be conducted together with a follow-up visit approximately 18 days after the last dose of study intervention, as shown in the SoA. See SoA for data to be collected at the time of study discontinuation and follow-up and for any further evaluations that need to be completed. A participant who is withdrawn from the study for any reason related to safety (listed in Section [7.1](#) or otherwise) will continue to be followed up to assess the outcome of the safety event that triggered discontinuation of study drug. If a participant is unable to return to the clinic for any reason, site staff are encouraged to contact the participant for assessment of AEs.

The participant will be permanently discontinued from the study intervention and the study at that time.

All data and samples collected up to and including the date of withdrawal of/last contact with the participant will be included in the study analyses. If the participant withdraws consent for disclosure of future information, the sponsor may retain and continue to use any data collected before such a withdrawal of consent.

If a participant withdraws from the study, the participant may request destruction of any samples taken and not tested, and the investigator must document this in the site study records.

The primary reason for participant discontinuation/ withdrawal from the study will be documented in the eCRF based on the list below:

| Reasons | Additional items/Sub-reasons |
|--|--|
| AE | Unsolicited AE Solicited AE |
| Lost to follow-up | Subject Relocated Subject was Incarcerated Other, specify Unknown |
| Participant Reached Protocol-Defined Stopping Criteria | Liver Event QTc Laboratory Abnormality |
| Physician Decision | Loss of ability to freely provide consent due to treatment of either a psychiatric or physical condition |
| Pregnancy | |
| Protocol Deviation | Repeat non-adherence of participant with protocol requirements or treatment |
| Site Terminated by Sponsor | |

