8.2.1. HIV-1 RNA Sampling

Plasma for quantitative HIV-1 RNA will be generated at timepoints listed in the SoA (Section 1.3).

An HIV-1 RNA PCR assay with a LLOD of 40 copies/mL or lower will be used.

Details concerning the handling, labeling, and shipping of these samples will be provided in the laboratory manual.

In order to maintain the blind, HIV-1 RNA results will not be provided to site staff.

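### A site-level code break ends study participation even when no dose remains; in the single-dose cohorts this can cost viral load and 168-hour PK data up to Day 8

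*Protocol*

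**What the plan says.** Protocol 6.4 lets the investigator break the code in an emergency and puts participant safety first in that decision. It then adds: "A participant will be withdrawn if the participant's intervention code is unblinded by the investigator or treating physician". No study day, dosing status or exception is attached. Protocol 7.2 sets the scope of a withdrawal: "The participant will be permanently discontinued from the study intervention and the study at that time".

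Section 7.2 also limits the damage:
- "At the time of discontinuing from the study, if possible, an ED visit should be conducted together with a follow-up visit approximately 18 days", counted from the final dose.
- "All data and samples collected up to and including the date of withdrawal of/last contact with the participant will be included" in the analyses.
- A participant withdrawn for a safety reason "will continue to be followed up to assess the outcome of the safety event that triggered discontinuation of study drug".

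Assignment can also reach the site another way. When the sponsor's safety staff unblind an SAE that needs expedited reporting, a copy of the report "identifying the participant's intervention assignment, may be sent to investigators in accordance with local regulations". Section 6.4 attaches no withdrawal to that route.

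On the endpoints, Protocol 3.1 takes the primary endpoint through Day 8. Its secondary PK list includes "Following single dose: Cmax, tmax, AUC(0-168) and C168". Protocol 8.2.1 keeps viral load from sites: "In order to maintain the blind, HIV-1 RNA results will not be provided to site staff". Protocol 8.5 does the same for drug concentrations that could unblind. SAP 4.2.2 does not impute missing HIV-1 RNA and takes the nadir from whatever values exist.

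**The concern.** A withdrawal rule tied to unblinding makes sense where later data would be coloured by knowledge of treatment, or where a dosing decision is still open. After the last planned dose there is no dosing decision. Viral load and drug concentration are laboratory measurements withheld from the site, so ending their collection does not protect them.

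The single-dose cohorts are most exposed, because dosing ends on Day 1 while the primary and PK endpoints run to Day 8. Four consequences follow for a participant unblinded in that interval:
- The nadir may come from an early sample, which understates the decline for someone who stays in the FAS.
- A missing Day 8 HIV-1 RNA value removes the participant from the per-protocol set (SAP Table 1, criterion 03).
- C168 and AUC(0-168) may be unobtainable.
- If the discontinuation counts as a safety concern, SAP 4.1.1 bars replacement.

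The protocol already separates stopping drug from stopping data in one setting. Appendix 6 (10.6) keeps participants in the study for protocol follow-up after a liver stopping event.

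**Working it through.** **Step 1. What is at risk, by cohort and timing.** The Schedule of Activities has five post-baseline HIV-1 RNA samples up to Day 8 (Day 2, Day 3 or 4, Day 5 or 6, Day 7, Day 8), then Days 14, 21 and 25.

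| Code break | Doses left | Scheduled data at risk | What an early-discontinuation visit can recover |
|---|---|---|---|
| Single dose, after Day 1 dose and before Day 8 | None | Up to 5 HIV-1 RNA values; C168; AUC(0-168) | One HIV-1 RNA value and one PK sample; not C168 if held before 168 h |
| Once daily, during dosing | Some | As above, with Day 7 PK | Little separate effect where a dose is missed: Protocol 7.1.4 then requires withdrawal anyway (part of that sentence is redacted) |
| Once daily, after Day 7 dose | None | Day 8 HIV-1 RNA and 24 h PK; Days 14 and 21 | The Day 8 items, if held on Day 8 |
| Any cohort, after Day 8 | None | Mainly Days 14 and 21 and exploratory AE collection | Primary endpoint already complete |

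**Step 2. The 18-day visit.**
- Once daily: Day 7 + 18 = Day 25, the planned final visit.
- Single dose: Day 1 + 18 = Day 19. That is too late for the primary endpoint or C168 and 6 days short of the Day 25 AE endpoint. It also lies between the SAP 6.3.3 windows of Days 13–15 and 20–22. The protocol says approximately 18 days, so the exact day may vary.

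**Step 3. Reproduce the plan's precision, then remove one participant.** Full width = 2 × t(0.975, n−1) × SD / √n.
- n = 6, t = 2.571: SD 0.40, 0.50, 0.65 and 0.80 give 0.84, 1.05, 1.36 and 1.68, matching Protocol Table 9.
- n = 5, t = 2.776, SD 0.65: 2 × 2.776 × 0.65 / 2.236 = 1.61. The range is 0.99 (SD 0.40) to 1.99 (SD 0.80).
- Ratio at SD 0.65: 1.614 / 1.364 = 1.18, so 18% wider.

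This applies only if the participant has no usable post-baseline value.

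**Step 4. Truncated nadir, illustration only.** Assume a linear decline of D log10 from Day 1 to Day 8, a last sample on Day L, and no later value. The participant's shortfall is D × (8 − L) / 7, and the shift in a six-person mean is one sixth of that.

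| Last sample | D = 1.0: participant / cohort mean | D = 2.0: participant / cohort mean |
|---|---|---|
| Day 2 | 0.86 / 0.14 | 1.71 / 0.29 |
| Day 4 | 0.57 / 0.10 | 1.14 / 0.19 |
| Day 7 | 0.14 / 0.02 | 0.29 / 0.05 |

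The values of D are assumptions; the documents give no expected decline.

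**The case against.** The other side has real force.

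- **The data are not simply lost.** A reader might infer that everything after the code break disappears. Section 7.2 does not support that: it asks for two further visits, keeps earlier data and follows the triggering event. The follow-up/ED column includes HIV-1 RNA, PK, ECG, vital signs and laboratory tests, and SAP 6.3.3 slots withdrawal-visit values into analysis visits. What stands against this is that the two visits are conditional, and one early visit cannot replace a series running to 168 h.
- **Unblinding can bias some of the data.** A reader might extend the laboratory argument to all safety data. Protocol 4.2 justifies the placebo by blinded assessment of AE relatedness, so AE reporting, grading and causality after a code break are open to bias. The point holds only for laboratory measurements.
- **Other rules already remove many of these participants.** Events serious enough to prompt a code break may meet the stopping criteria in 7.1 to 7.1.3, and 7.1 ends participation when treatment is permanently discontinued. The rule acts alone only when no other withdrawal rule applies. This narrows the point in every cohort, most of all during once-daily dosing.
- **PK after stopping treatment is excluded from summaries anyway** (SAP 4.3.1.3). But Protocol 7.1 defines discontinuation as not receiving all planned doses, and a single-dose participant has received them.
- **The trial is descriptive and events should be rare.** Protocol 2.2.1.1 reports no SAE and no Grade 3 or 4 AE on active drug in the first-in-human study, and the design accepts five evaluable participants per active cohort. This limits the priority, not the logic.

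**Conclusion.** The concern holds in a limited form. The rule is automatic, has no time limit and applies after the last dose. Its clearest cost is in the single-dose cohorts between the Day 1 dose and Day 8, where it can shorten the nadir series and forgo C168 and AUC(0-168) although no dose remains. In once-daily cohorts the separate effect is mainly after Day 7. After Day 8 the primary and secondary endpoints are essentially complete.

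No expected loss can be stated, because the documents give no code-break rate. Conditional on one code break, a participant with no usable post-baseline value widens the interval by 18%. A last sample on Day 4 shifts a six-person mean by 0.10 to 0.19 log10, if decline is linear and no later value is obtained. The documents do not support reading that shift as a forecast: an early-discontinuation sample would shrink it, and linear decline is not established. The estimand tables are redacted, so the strategy for withdrawal cannot be checked. This is an inexpensive improvement, not a threat to the trial's conclusions.

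**What to change.** State in Protocol 6.4 and 7.2 that a code break does not by itself end data collection. The participant is asked to complete the scheduled HIV-1 RNA, PK, resistance and safety assessments through Day 25, subject to consent. In the SAP, flag AE causality and grading assessed after unblinding so that they can be read separately.

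Two limits matter. An emergency code break that 6.4 authorises should not be classed as a protocol deviation; that would also draw the participant into the adjudication under SAP Table 1, criterion 08. Any consequence for remaining doses should be reconciled by the sponsor across Protocol 6.4, 7.1, 7.1.4 and 7.2; this point proposes no dosing rule.

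The cost is protocol wording and one flag. The downside is that the participant's AE assessments after the code break are not blinded, as can already happen when a sponsor-unblinded SAE report reaches the investigator. Participants withdrawn under other stopping rules are not helped. SAP 4.7 notes that the interim analysis has taken place and Part 2 will proceed, so new wording can help only participants not yet through the study; for Part 1 the sponsor can report how many code breaks occurred.
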